## 7.5.3 Exploratory Efficacy Analyses

### Protocol Specified Exploratory Efficacy Analyses

The change from baseline in Hurley Stage, HS-PGA, HS-PtGA, PGI-B, and PGI-S will be summarized in shift tables. In the shift table, for each treatment, the counts and percentages will be shown for baseline values crossed with each post-baseline time point. Agreement between the baseline score and each post-baseline score will be estimated with a weighted Kappa coefficient and corresponding 90% CI (Cohen, 1968) A test of treatment difference for agreement will be done separately for each treatment group and will consist of a CMH test (ANOVA for row means) applied to a 2x2xR table (baseline Hurley Stage x treatment x agreement score), where the agreement score is the Cicchetti-Allison weight (Cicchetti, 1971) used for the weighted Kappa coefficient, which is  $1 - \text{difference}/(R-1)$  where R is the number of categories in the endpoint.

The change from baseline and percent change (shown as \*) from baseline in each continuous exploratory variable (AN count\*, abscess count, inflammatory nodule count, draining fistula count at each visit, calculated composite of abscess, inflammatory nodule and draining fistula count, calculated composite of abscesses, draining fistulas, and inflammatory and non-inflammatory nodules, HS Pain NRS\* at visits other than Week 16, worst HS pain NRS, DLQI scores at each visit, IHS4 score at each visit, HiSQOL score at each visit ) will be analyzed using a similar MMRM model as described for the primary efficacy analysis in **Section 7.5.1**, but changing baseline AN count to baseline of the outcome. Summary statistics and the results of statistical testing at each visit will be provided for each continuous exploratory variable.

The frequency and percentage of subjects for each categorical exploratory variable (proportion of subjects achieving AN50 and AN75 responses, percentage of subjects experiencing flare, proportion of subjects achieving HiSCR50 and HiSCR75 at each visit, proportion of subjects achieving HS-PGA of inactive (0) or almost inactive (1) at each visit, proportion of subjects achieving at least 2-point decrease in HS-PGA at each visit, proportion of subject with a 2 point reduction from baseline on HS-PGA at each visit, proportion of subjects achieving a 3-point reduction on the HS Worst Pain NRS for subjects with baseline HS Worst Pain NRS of at least 3, proportion of subjects achieving a 3-point reduction on the HS Average Pain NRS

for subjects with baseline HS Average Pain NRS of at least 3, proportion of subjects requiring rescue medication or treatment at each visit, proportion of subjects in each response category for the HS-PtGA at each visit, proportion of subjects in each response category for the PGI-C at each visit, proportion of subjects achieving much improvement in PGI-C at each visit, proportion of subjects achieving improvement at each visit, proportion of subjects in each response category for the PGI-S at each visit, proportion of subjects achieving “Mild” or “No activity” / “Clear skin” for the PGI-S at each visit, proportion of subject in each response category for the PGI-B at each visit, proportion of subjects achieving “A little bothered” or “Not at all bothered” for the PGI-B at each visit, proportion of subjects in each category of Hurley Stage at each visit, proportion of subjects achieving at least a 1-stage improvement (decrease) in Hurley Stage will be summarized at each visit.

For PGI-S, PGI-B, HS-PtGA, HS-PGA, and PGI-C, the difference in distribution between the imsidolimab and placebo groups will be compared separately for each treatment group by using a Wilcoxon rank-sum test and Somers' d statistic, which may be interpreted as a generalized risk difference ([Edwardes, 2000](#)). This will be performed over all subjects for each comparison, and within each stratum for Hurley Stage. The difference in distribution between the imsidolimab and placebo groups (stratified by baseline Hurley Stage) will be compared using a Cochran-Mantel-Haenszel test as described in **Section 7.5.2.2**. For PGI-S, PGI-B, HS-PtGA, and HS-PGA, the change from baseline will also be analyzed using an ordinal logistic regression model with treatment and baseline Hurley Stage as categorical covariates. Odds ratios resulting from this model along with 90% CI will be reported. The proportional odds assumption will also be tested, and the corresponding p-value will be reported.

### Additional Exploratory Efficacy Analyses

To estimate the treatment effect while accounting for a subject knowing they are on study drug, the primary endpoint analysis will be repeated comparing the estimated change from Day 1 imsidolimab baseline to Week 16 (for active dose subjects in the placebo-controlled period) to the estimated change from Week 16 imsidolimab baseline to Week 32 (for placebo → imsidolimab subjects). This comparison will be done separately for like doses (arm 1 to arm 3A, and arm 2 to arm 3B.)

To further estimate the treatment effect while accounting for a subject knowing they are on study drug and while also accounting for inter-subject variability, the primary endpoint analysis model as described in **Section 7.5.1**, will be fitted. A binary indicator variable will be added to the model to indicate visits at which the subject knows they are on study drug. The change from imsidolimab baseline between Week 16 and Week 32 for the placebo → imsidolimab group will be compared within treatment regimen. The overall treatment effect at 16 weeks will be estimated with the primary independent group contrast at Week 16 as well as the cross-over contrast between Week 16 and Week 32 for the placebo → imsidolimab group. Furthermore, the effect of 32 weeks of exposure compared to 16 weeks of exposure will be estimated comparing like doses.

The change from baseline and percent change from baseline in the calculated composite total of abscess, inflammatory nodule, and draining fistula count at each visit, and percent change from baseline in the draining fistula count at each visit will be analyzed using a similar MMRM model as described for the primary efficacy analysis in **Section 7.5.1**, but changing baseline AN count to baseline of the outcome variable and adding Hurley Stage at baseline as an additional covariate. Summary statistics and the results of statistical testing at each visit will be provided for each continuous exploratory variable.

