## STATISTICAL ANALYSIS PLAN FOR STUDY ANB019-208

**Trial Sponsor:** AnaptysBio, Inc.  
**Protocol Number:** ANB019-208  
**IND Number:** 136145  
**EUDRACT Number:** TBD  
**Investigational Drug:** Anti-interleukin 36 receptor monoclonal antibody  
**Indication:** Hidradenitis Suppurativa  
**Drug Number:** ANB019 (imsidolimab)  
**Dosage Form/Strength/Dose:** 2 mL Solution for Injection/200 mg/400 mg, 2 mL Solution for Injection/200 mg/200 mg, 2 mL Solution for Injection/100 mg/200 mg, or 2 mL Solution for Injection/100 mg/100 mg.

- Arm 1: Imsidolimab 400 mg on Day 1; 200 mg on Day 29, 57 and 85; 200 mg on Day 113; followed by 200 mg on Days 141, 169 and 197.
- Arm 2: Imsidolimab 200 mg on Day 1; 100 mg on Days 29, 57 and 85; 100 mg dose on Day 113; followed by 100 mg on Days 141, 169 and 197.
- Arm 3A: Placebo on Days 1, 29, 57, and 85; imsidolimab 400 mg on Day 113; followed by 200 mg on Days 141, 169, and 197.
- Arm 3B: Placebo on Days 1, 29, 57, and 85; imsidolimab 200 mg on Day 113; followed by 100 mg on Days 141, 169 and 197.

**Protocol Title:** A Phase 2, Randomized, Double-Blind, Placebo-Controlled Study to Evaluate the Efficacy and Safety of Imsidolimab (ANB019) in the Treatment of Subjects with Hidradenitis Suppurativa

**Version:** V1.0  
**Sign-off Date:** 16-Aug-2022  

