## 3. STUDY DESIGN

### 3.1 Study Design

This study is a Phase 2, multicenter, randomized, double-blind, placebo-controlled study to evaluate the efficacy and safety of imsidolimab in adult subjects with hidradenitis suppurativa (HS). This study will also characterize the pharmacokinetic (PK) profile of imsidolimab and explore the immune response to imsidolimab in subjects with HS.

To be eligible for this study, subjects must have a clinically confirmed diagnosis of HS with a disease duration of at least 6 months before Day 1. In addition, subjects will have the following characteristics at Screening and Day 1:

- 1) HS lesions present in at least 2 distinct anatomical areas, 1 of which must be Hurley Stage II (i.e., single or multiple, widely separated, recurrent abscesses with tract formation and cicatrization) or Hurley Stage III (i.e., diffuse or near diffuse involvement, or multiple interconnected tracts and abscesses across the entire area);
- 2) total abscess and inflammatory nodule (AN) count of  $\geq 5$ ;
- 3)  $\leq 20$  draining fistulas.

Randomization will be stratified based on Hurley Stage at baseline (Stage II or III).

The maximum study duration per subject is approximately 44 weeks, which includes a screening period of up to 30 days, followed by a 16-week placebo-controlled period, a 16-week treatment extension period, and an 8-week follow up period. The placebo-controlled period ends at Day 113 (Week 16) and the treatment extension period starts when study treatment is administered at the Week 16 visit. Of note, during the extension period all subjects will receive imsidolimab but their treatment will remain blinded.

During the placebo-controlled period, eligible subjects will be randomized (1:1:1) to receive either imsidolimab (at 1 of 2 different regimens) or placebo, subcutaneously (SC) administered on 4 occasions: Day 1, Day 29 (Week 4), Day 57 (Week 8), and Day 85 (Week 12).

The treatment arms during the placebo-controlled period will be as follows:

[figure not shown]
- Imsidolimab 400 mg on Day 1, followed by 200 mg on Days 29, 57, and 85
- Imsidolimab 200 mg on Day 1, followed by 100 mg on Days 29, 57, and 85
- Placebo on Days 1, 29, 57, and 85

During the extension period, all subjects will receive imsidolimab, SC administered on 4 occasions:

- 400 mg dose of imsidolimab on Day 113 for subjects assigned to placebo arm 3A during the placebo-controlled period, followed by 200 mg doses on Days 141, 169, and 197

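### The extension comparison of Arm 1 with Arm 3A (and Arm 2 with Arm 3B) cannot estimate a treatment effect, because both sides of each pair receive the same regimen

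*SAP*

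**What the plan says.** The first paragraph of Additional Exploratory Efficacy Analyses in SAP 7.5.3 gives its purpose as "To estimate the treatment effect while accounting for a subject knowing they are on study drug, the primary endpoint analysis will be repeated". One side is "the estimated change from Day 1 imsidolimab baseline to Week 16 (for active dose subjects in the placebo-controlled period". The other is "the estimated change from Week 16 imsidolimab baseline to Week 32 (for placebo → imsidolimab subjects". The pairing is by dose: "This comparison will be done separately for like doses (arm 1 to arm 3A, and arm 2 to arm 3B".

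SAP 3.1 gives the regimens. Arm 1 receives "Imsidolimab 400 mg on Day 1, followed by 200 mg on Days 29, 57, and 85". The extension entry for Arm 3A is "400 mg dose of imsidolimab on Day 113 for subjects assigned to placebo arm 3A during the placebo-controlled period, followed by 200 mg doses"; there are three of these lower doses, at Weeks 20, 24 and 28 (the last is Day 197). Arms 2 and 3B match each other in the same way at 200 mg and then 100 mg.

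SAP 3.1 also requires an AN count of at least 5, under the heading "subjects will have the following characteristics at Screening and Day 1". No such threshold applies at Week 16, where SAP section 6 simply resets the baseline of the former placebo subjects to the value before their first extension dose.

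**The concern.** A treatment effect needs a comparison between drug and no drug, or between different exposures. Here the drug, dose sequence and duration are the same on both sides, and no placebo interval enters the contrast. Whatever is estimated comes from the ways in which the two periods differ apart from drug:

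- **Blinded placebo response** belongs to the first period.
- **Regression to the mean** after selection on AN count bears on the Day 1 baseline and not on the Week 16 baseline.
- **Awareness of being on active drug** belongs to the extension.
- **Selection**: the former placebo side contains only subjects who reached Week 16 and were dosed there.

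These components cannot be separated from one another. A reader who takes the stated purpose at face value could credit an inert drug with benefit or harm, or conclude from a null result that an effective drug does nothing.

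**Working it through.** **1. The plan's own figure.** Inputs from Protocol 9.2 and SAP 3.5: 36 evaluable per arm, difference 4.9, SD 8.2, two-sided alpha 0.10. Noncentral-t power for the Week 16 comparison with placebo is 80.7%, which agrees with the stated 80%.

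**2. Same exposure on both sides.** Arm 1 has four doses (400, 200, 200, 200 mg) and is read at Day 113, which is 113 − 85 = 28 days after the fourth. Arm 3A has the same four doses and is read at Day 225, which is 225 − 197 = 28 days after the fourth. Arms 2 and 3B match likewise at 200, 100, 100, 100 mg.

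**3. Algebra.** Let D be the drug effect over 16 weeks, P1 the non-drug change from Day 1 to Week 16, and P2 the non-drug change from Week 16 to Week 32, including awareness. Negative values are improvement.

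- SAP contrast: (D + P1) − (D + P2) = P1 − P2. D is absent.
- Primary contrast, active versus concurrent placebo: (D + P1) − P1 = D.

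If the drug effect differs between periods, a drug-by-period difference is added, which is still not D.

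**4. Size without baseline adjustment.** The placebo arm is split 1:1 at Week 16 (SAP 3.2), so Arm 3A has about 36/2 = 18, assuming no further loss. SE = 8.2 × √(1/36 + 1/18) = 2.37, with 52 degrees of freedom. The documents give no placebo response, so P1 and P2 are assumptions.

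| P1 | P2 | Expected contrast | Chance of p < 0.10 |
|---|---|---|---|
| 0 | 0 | 0 | 10.0% |
| −2 | 0 | −2 | 21.5% |
| −4 | 0 | −4 | 51.0% |
| −6 | 0 | −6 | 80.4% |
| −4 | −2 | −2 | 21.5% |
| 0 | −2 | +2 | 21.5% |

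The table is the same for D = 0, −4.9 or −8, so the result does not distinguish an inert drug from an active one. The last row shows the sign reversing.

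**5. Size with baseline AN count as covariate.** The SAP repeats the primary analysis, and SAP 7.5.1 adjusts for baseline AN count. ANCOVA was simulated as a simplified stand-in for that model. Assumptions: mean AN 13, between-subject SD 7.0, within-subject SD 5.8 (5.8 × √2 = 8.2, the plan's SD of change), 36 versus 18 subjects, inert drug. Here P1 is the shift in underlying level, and regression to the mean comes on top of it.

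| P1 | P2 | Rejection, entry rule at Day 1 only | Rejection, entry rule at Screening and Day 1 |
|---|---|---|---|
| −2 | 0 | 22.0% | 18% |
| −4 | 0 | 36.5% | 32% |
| −6 | 0 | 54.3% | 46% |
| −4 | −2 | 13.4% | 11% |

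Under the Day 1 rule with D = −4.9, the first three rows become 22.9%, 37.9% and 54.7%. Adjustment shrinks the bias but does not bring D back. With P1 = P2 = 0, entry selection alone still leaves a mean adjusted contrast of −0.65 and 11.1% rejections. With P1 = 0 and P2 = −2 the adjusted mean is +1.28.

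**The case against.** The strongest defence is that this is one paragraph of exploratory work. SAP 3.3 treats comparisons beyond the primary endpoint as exploratory, and the efficacy conclusion rests on the concurrent randomised contrast in SAP 7.5.1. The second paragraph of the same subsection is a separate model, with an awareness indicator and the primary Week 16 contrast, and it also plans a comparison of 32 with 16 weeks of exposure. All of that stands, and it limits the severity.

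Four stronger readings are tempting, and the documents do not support them.

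- *That the contrast could drive the development decision.* SAP 3.4 ties that decision to an analysis run when all subjects have completed Week 16 or left, covering the primary and secondary efficacy endpoints. The disputed contrast needs Week 32 data.
- *That an inert drug is expected to show the placebo response.* The expectation is P1 − P2. It equals the placebo response only if P2 is zero, and awareness in the extension pushes the other way.
- *That 51% and 80% are the plan's error rates.* They come from an unadjusted t-test with P2 = 0. The planned model adjusts for baseline, and the adjusted rates are lower.
- *That the output table will carry a treatment-effect label.* The mock-ups are in a separate document (SAP Appendix 3). Only the purpose clause can be seen.

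None of this restores D to the contrast.

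**Conclusion.** The point holds as a minor one: followed as written, this analysis does not estimate what it says it estimates. Exact cancellation rests on a drug effect that is additive and equal in the two 16-week intervals.

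The direction of the error is not fixed. An inert drug may look active or harmful, and an effective one may show nothing. For an inert drug with assumed first-period falls of 2, 4 or 6 lesions and P2 = 0, false-positive rates under baseline adjustment are about 18–22%, 32–37% and 46–54% against a nominal 10%. They fall towards 10% as P2 moves from zero towards P1. These rates depend on assumed P1, P2 and AN distribution, and on 18 subjects remaining in Arm 3A at Week 32, although the plan's 10% dropout covers only the time before Week 16.

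**What to change.** Remove the treatment-effect purpose from the first paragraph. If the contrast is kept, call it the difference in 16-week response between blinded first-period use and extension use, and say that awareness, period, regression to the mean and attrition are combined in it.

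If a treatment-related estimate from the extension is wanted, add the concurrent randomised contrast: change from Week 16 to Week 32 in Arm 3A minus the same change in Arm 1, and 3B minus Arm 2. For an inert drug its expected value is zero, apart from differential dropout. Describe it as placebo-arm catch-up. State that it equals the Week 16 effect only if:

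- the imsidolimab arm has plateaued by Week 16;
- the response to awareness is equal in both arms;
- the floor at zero lesions does not limit further change.

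The cost is a few sentences and one contrast statement per dose, with no new data. The catch-up contrast answers a delayed-start question and partly overlaps the exposure comparison already planned in the second paragraph, so the two should be aligned.

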#### 9.4.5 ANALYSIS OF THE PRIMARY EFFICACY ENDPOINT

The primary efficacy endpoint is the change from Baseline in AN count at Week 16.

The primary estimand, comprising four components, is defined as follows:

- a) The target population consists of subjects with hidradenitis suppurativa who are eligible to be included in the clinical trial based on the inclusion/exclusion criteria in the protocol. The ITT analysis set will include all randomized subjects. For the analysis, treatment will be assigned based upon the treatment arm to which subjects are randomized regardless of which treatment they receive.
- b) The primary variable is the change from baseline in AN count of an individual subject at Week 16.
- c) To handle intercurrent events such as use of rescue medications, the hypothetical strategy for estimand will be used. Data collected following receipt of rescue medication (if any) will be considered missing in the analysis.
- d) The population-level summary measures will be the population mean differences in the primary variable between each dose of imsidolimab and placebo at Week 16.

A general linear mixed effects model for repeated measures (MMRM) analysis will be used to estimate the least squares means (LSM) and associated standard errors for the change from Baseline in AN count to Week 16. The model will include change from Baseline in AN count at Week 16 as the dependent variable, fixed effects for treatment arm, categorical time point, and the treatment by time point interaction, and the Baseline AN count and stratification factor (ie, Hurley Stage at baseline (Stage II or III)) as covariates. An unstructured covariance structure will be used. The difference between LSMs (imsidolimab – placebo) at Week 16 will be presented along with the associated 90% CI and p-value. The ITT analysis set will be used for the primary efficacy analysis.

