**Figure 1 Study Schema**

Abbreviations: D, day; SC, subcutaneously; W, week.

a During the placebo-controlled period, subjects will be randomized (1:1:1) to receive either imsidolimab (at 1 of 2 different regimens) or placebo, SC administered on 4 occasions: 1) 400-mg dose of imsidolimab on Day 1, 200-mg dose of imsidolimab on Days 29, 57, and 85; 2) 200-mg dose of imsidolimab on Day 1, 100-mg dose of imsidolimab on Days 29, 57, and 85.

b The placebo-controlled period ends on Day 113 (week 16) visit, before study treatment administration. Pre-dose assessments performed on Day 113 (week 16) will be used to evaluate the primary and secondary efficacy endpoints, as well as the safety, tolerability, and immune response of imsidolimab compared with placebo. The extension period starts when the study treatment is administered on Day 113 (week 16) visit. All subjects will receive imsidolimab SC administered on 4 occasions during the extension period.

c Subjects in Arm 3 randomized to placebo during the placebo-controlled period will be randomized 1:1 to receive either a 400-mg dose of imsidolimab on Day 113, followed by a 200-mg dose on Days 141, 169, and 197; or a 200-mg dose of imsidolimab on Day 113, followed by a 100-mg dose of imsidolimab on Days 141, 169, and 197. Subjects randomized to imsidolimab in Arms 1 and 2 during the placebo-controlled period will continue to receive the same maintenance dose of imsidolimab (200 mg or 100 mg) on Days 113, 141, 169, and 197.

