## 6.2 Efficacy

Endpoints analyzing the placebo-controlled data will use the last pre-dose assessment for all visits and for all study arms. The extension period starts at the Week 16 dose, and endpoints analyzing the extension period data will include pre-dose results from Week 16 as the imidolimab baseline for the placebo arms, as well as pre-dose results from Weeks 20, 24, and 28, and follow-up results (no dose) from Weeks 32, 36, and 40 for all study arms.

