#### 7.5.1 Primary Efficacy Estimand

The primary estimand, comprising five components, is as follows:

- a) The target population is subjects in the United States and Europe diagnosed for at least 6 months with HS, having lesions at Hurley Stage II or III.
- b) The primary variable is the change from baseline in AN count of an individual subject at Week 16.
- c) To handle intercurrent events such as use of rescue medications, a hypothetical strategy for estimand (**ICH E9, 2019**) will be used such that data collected following receipt of rescue medication (if any) will be considered missing in the analysis. Missing values will be imputed as described in **Section 7.5.4**. The hypothetical scenario envisaged under this estimand is what value the primary variable would have taken if the subject had not taken rescue treatment.

- d) The population-level summary measure for the primary endpoint is mean change from baseline in AN count at Week 16. The estimator for between-group comparison of the primary endpoint will be the difference in the primary endpoint between imidolimab and placebo at Week 16.
- e) The treatment conditions of interest, two imidolimab treatment regimens and one placebo regimen:
  1. Imsidolimab 400 mg injection on Day 1, followed by 200 mg on Days 29, 57, and 85;
  2. Imsidolimab 200 mg injection on Day 1, followed by 100 mg on Day 29, 57, and 85;
  3. Placebo on Days 1, 29, 57, and 85

A linear mixed model will be used for the repeated measures (MMRM) with treatment, visit, treatment by visit interaction, and Hurley Stage at baseline as a categorical covariate and baseline AN count as a continuous covariate. An unstructured correlation (UN) matrix will be used to model correlation within a patient; if convergence is an issue, a Toeplitz structure may be considered. If convergence issue persists, elimination of post-baseline visits other than Week 16 may be considered. Subjects with missing data at Week 16 due to early discontinuation will be included in the model.

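### In the second awareness analysis of SAP 7.5.3, the awareness indicator is aliased with visit, so the awareness-adjusted cross-over contrast cannot be estimated

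*SAP*

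**What the plan says.** The additional exploratory part of SAP 7.5.3 contains two analyses meant to allow for subjects knowing they receive active drug.

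- The first compares 16-week changes from imsidolimab baseline between like doses: Arm 1 with Arm 3A, and Arm 2 with Arm 3B. It uses no indicator.
- The second, the subject of this point, is a model: "the primary endpoint analysis model as described in Section 7.5.1, will be fitted". To it the SAP adds one term: "A binary indicator variable will be added to the model to indicate visits at which the subject knows they are on study drug". From this fit it plans both the Week 16 contrast between arms and a cross-over contrast from Week 16 to Week 32 in subjects who switched from placebo.

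SAP 7.5.1 defines the base model as "repeated measures (MMRM) with treatment, visit, treatment by visit interaction, and Hurley Stage at baseline as a categorical covariate", with baseline AN count as a continuous covariate. Protocol 9.4.5 confirms that time is categorical: "fixed effects for treatment arm, categorical time point, and the treatment by time point interaction". The Appendix 2 template likewise declares visit as a class variable.

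Three statements fix when awareness changes:

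- SAP 3.1: "during the extension period all subjects will receive imsidolimab but their treatment will remain blinded".
- SAP 6.2: "The extension period starts at the Week 16 dose".
- SAP Figure 1: "The placebo-controlled period ends on Day 113 (week 16) visit, before study treatment administration".

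SAP 6.2 lists the later assessments as "pre-dose results from Weeks 20, 24, and 28, and follow-up results (no dose) from Weeks 32, 36, and 40 for all study arms".

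**The concern.** An awareness effect can be separated from a visit effect only if, at some visit, some subjects know they are on drug and others do not. This design has no such visit. Before the Week 16 dose nobody knows. Afterwards everybody knows they are on imsidolimab, although the regimen stays blinded. The indicator therefore repeats what the visit terms already carry.

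What is at stake is the purpose of this one analysis. Protocol 4.2 describes HS efficacy assessments as highly subjective, so an expectation effect after Week 16 is a reasonable worry. The SAP offers the cross-over contrast alongside the randomized Week 16 contrast as an estimate of the 16-week treatment effect. Without a working adjustment, it is a within-group change that also contains awareness and calendar time.

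**Working it through.** The documents give no figure for this analysis, so there is no stated number to reproduce. The check is on the fixed-effects design.

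**Inputs.** Four arms (1, 2, 3A, 3B) and ten post-baseline visits (Weeks 4, 8, 12, 16, 20, 24, 28, 32, 36, 40), with treatment, visit and treatment by visit as class effects (SAP 7.5.1, SAP 6.2, protocol 9.4.5).

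**Step 1: the indicator.** Let V(w) be the dummy for week w. Under the planned schedule, in every arm,

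indicator = V(20) + V(24) + V(28) + V(32) + V(36) + V(40).

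It is an exact sum of columns already in the model.

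**Step 2: rank.** A term is estimable only if adding it raises the rank of the design matrix.

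| Design | Rank without | Rank with |
|---|---|---|
| Arm by visit, 4 × 10 | 40 | 40 |
| Main effects only, 1 + 3 + 9 | 13 | 13 |
| Arm by visit to Week 32, 4 × 8 | 32 | 32 |

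Baseline AN count and Hurley Stage add 2 to each figure (42, 15, 34) and change nothing else. Treating placebo as one arm gives 32 and 32 with those covariates. Replacing arm by current treatment, still crossed with calendar visit, gives 26 and 26 with them. The gain is zero in each case.

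**Step 3: which contrasts survive** in the four-arm model with the indicator:

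- Awareness coefficient: not estimable.
- Arm 3A, Week 32 minus Week 16 with awareness held equal: not estimable.
- Arm 3A, Week 32 minus Week 16 with awareness moving from 0 to 1 (the raw change): estimable.
- Arm 1 minus Arm 3A at Week 16: estimable, because the indicator is the same for both arms and cancels.

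**Step 4: whether another model identifies it.** Replace calendar visit by weeks on the current regimen, with one set of terms per regimen shared by Arms 1 and 3A and by Arms 2 and 3B. Using all visits, the cells are 4 placebo + 10 + 10 = 24, and the indicator raises the rank to 25. Using visits to Week 32, they are 4 + 8 + 8 = 20, and the rank rises to 21. If calendar visit is kept as well, the all-visits design has rank 30 with and without the indicator, so visit must be replaced, not supplemented.

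**Step 5: what that coefficient is.** In ordinary least squares with equal cell sizes, it is the mean of eight differences: (3A minus 1) and (3B minus 2) at each of weeks 4, 8, 12 and 16 on drug. All other visits get zero weight. A repeated-measures fit would weight these differently, but the identifying comparison is the one already planned in the first paragraph.

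**Step 6: why stop at Week 32.** Weeks 20 and 24 on regimen fall at calendar Weeks 20 and 24 in Arms 1 and 2, which are extension dosing visits. In Arms 3A and 3B they fall at calendar Weeks 36 and 40, which are follow-up visits after the last dose on Day 197. Sharing terms there would equate on-treatment and off-treatment means.

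**The case against.** The strongest reply is that little depends on this. It is the second of two supplementary analyses, absent from the protocol's list of exploratory endpoints, and it affects no primary or secondary result. That is correct and limits the importance of the point.

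A reader might infer that the SAP has lost any means of addressing awareness, or that the Week 16 treatment effect is compromised. The documents support neither. The first-paragraph comparison does not use the indicator and can be computed, and the Week 16 contrast is unchanged.

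A reader might also infer that the software will silently drop the term and an unadjusted result will be reported as adjusted. That does not follow. Which redundant column is dropped depends on term order. The Appendix 2 template works through LS means; with the indicator held at a common value, the Week 32 minus Week 16 difference is non-estimable, so the failure may well show in the output. The raw change appears only if a contrast lets the indicator change with visit.

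The aliasing is exact only on the planned schedule. SAP 6.2.1 allows a post-dose value when no pre-dose value exists, and protocol 7.1 lets subjects stop treatment and stay in the study. Such records could break the aliasing numerically, but the coefficient would then rest on a few non-random observations.

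Finally, the paragraph refers to comparison within regimen and to like doses, which may hint at regimen grouping, and Appendix 2 contains no code for this model. However, the text names the 7.5.1 model and gives no re-indexing of time. SAP 1 allows flexibility, but SAP 3.4 sends unblinded Week 16 results to sponsor management, so the model is better settled beforehand.

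**Conclusion.** The point holds for the second-paragraph model only. Under the planned visit schedule and the SAP 7.5.1 fixed effects, the indicator contributes no rank (40 and 40). The awareness coefficient and the awareness-adjusted Week 16 to Week 32 contrast are not estimable; what remains is the raw change. This is more than missing detail, because the rule as stated cannot do what the paragraph says it is for. It should be corrected, but it does not threaten the trial's main inference.

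The conclusion assumes that subjects understand the design, so that awareness begins with the Week 16 dose in all arms. It needs no assumption about effect size, variance or dropout.

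**What to change.** Preferred: delete the indicator and the statement that this model accounts for awareness, label the Week 16 to Week 32 cross-over contrast as unadjusted, and rely on the first-paragraph comparison of Arm 1 with 3A and Arm 2 with 3B.

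If a model is kept, the SAP should:

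- replace calendar visit by regimen crossed with weeks on the current regimen, shared by Arms 1 and 3A and by Arms 2 and 3B;
- use data only to Week 32 (rank 20 to 21);
- use the imsidolimab baseline defined in SAP 6 for visits after the switch;
- state that the coefficient combines awareness with calendar-time and prior-placebo effects, and assumes the same exposure-time profile in early and delayed starters.

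The cost is one SAP paragraph and, if a model is kept, its code. The downside of keeping it is dependence on that last assumption, for an estimate that draws on the same comparison as the first paragraph.
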